5.3. Variables

5.3.1. Exposures

The exposure of interest is the BNT162b2 XBB.1.5 mRNA vaccine. *In the event that XBB uptake is low, we will instead examine BA.4/5 vaccine effectiveness* (Section 5.5).

Information on vaccination status will continue to be collected on or after the authorization/approval date, therefore vaccination status will be considered as a time-varying exposure. Patients will be assigned as vaccinated or unvaccinated according to their vaccination status by each person-time record during the follow-up. A patient will be considered vaccinated from 14 days after their BNT162b2 vaccination date till the remainder of their follow-up.

The source of the exposure variables are the California and Louisiana vaccine registries and the HV (HealthVerity) Claims database. Clinical Vaccines Administered code (CVX), National Drug Codes (NDC) and Current Procedural Terminology® (CPT) codes used to identify the XBB.1.5 and BA.4/5 vaccinations are listed in the Protocol Annex.

XBB vaccinations will be enumerated using the following hierarchical definition:

- 1. Any person in HealthVerity claims data who has a record in the California/Louisiana Immunization Registry with a CVX code indicating having received the BNT162b2 XBB.1.5 monovalent mRNA vaccine will be considered vaccinated 14 days after registry event date.
- 2. Any person in HealthVerity claims data who has a record in the California/Louisiana Immunization Registry with an event indicating having received the BNT162b2 XBB.1.5 monovalent mRNA vaccine will be considered vaccinated 14 days after registry event date.
- 3. Any person in HealthVerity claims data who does not have a record in the California/Louisiana Immunization Registry but has a pharmacy claim with an NDC code indicating a BNT162b2 XBB.1.5 monovalent mRNA vaccine dose will be considered vaccinated 14 days after claim date.
- 4. Any person in HealthVerity claims data who does not have a record in the California/Louisiana Immunization Registry and does not have a pharmacy claim with an NDC code indicating a BNT162b2 XBB.1.5 monovalent mRNA vaccine dose but has a medical claim with a CPT code indicating a BNT162b2 XBB.1.5 monovalent mRNA vaccine dose will be considered vaccinated 14 days after claim date.

5. Any person in HealthVerity claims data who does not have a record in the California/Louisiana Immunization Registry, does not have a pharmacy claim with an NDC code indicating a BNT162b2 XBB.1.5 monovalent mRNA vaccine dose and does not have a medical claim with a CPT code indicating a BNT162b2 XBB.1.5 monovalent mRNA vaccine dose will be considered BNT162b2 XBB.1.5 unvaccinated.

BA.4/5 vaccinations will be enumerated in the same manner as XBB.1.5.

While XBB boosters are authorized for immunocompromised persons that are at least 2 months after first XBB dose, as well adults age 65+ at least 4 months after first XBB dose, only the first XBB vaccination will be analyzed. If a patient has multiple XBB.1.5 vaccination records, they will be censored at second dose.

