8.5. Study Size

Since the current study utilizes retrospective deidentified data without ability to recruit to a target, sample size calculations are not applicable. Further, this is a descriptive study without *a priori* specified hypotheses.

Initial data feasibility work has revealed approximately 19 million persons in the state of California with claims available in HealthVerity, among which approximately 25% are pediatric and 75% adult. Among these, approximately 12 million have at least one year of continuous medical and pharmacy enrollment. By end of 2023, we expect to have finished contracting to add approximately 565,000 additional persons. The proportion of these additional persons who will have 1-year continuous enrollment, and therefore the sample size estimates below have taken the conservative approach to not yet include these people.

We have identified 63% of persons in the claims data have at least one COVID-19 vaccine, and 16% received at least one bivalent dose. The claims population we have is not a random sample of Californians and may differ from the state's population in systematic ways (e.g. the age distribution). While differences may exist, we have high confidence in our ability to represent vaccination status for the individuals in our claims population.

We expect to begin to see XBB doses in data delivered in November 2023. Assuming uptake similar to that seen with the BA.4/5 vaccine, and non-differential uptake by age groups, we could anticipate in California:

(25% of 12 million are pediatric)*(16% uptake)*(60% of doses were Pfizer-BioNTech)

~ 288,000 pediatric XBB doses in California

(75% of 12 million are adult)*(16% uptake)*(60% of doses were Pfizer-BioNTech)

~ 864,000 adult XBB doses in California

Additional doses will be observed in Louisiana. In order to maintain patient de-identification, outcomes, covariates and subgroups will have at least 10 people in each category for inclusion in outputs. Throughout the protocol, this is referred to as "If sample size allows".

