- 5. Any person in HealthVerity claims data who does not have a record in the California/Louisiana Immunization Registry and does not have a pharmacy claim with an NDC code indicating a BNT162b2 XBB.1.5 monovalent mRNA vaccine dose but has a medical claim with a CPT code indicating a BNT162b2 XBB.1.5 monovalent mRNA vaccine dose will be considered vaccinated 14 days after claim date.
- 6. Any person in HealthVerity claims data who does not have a record in the California/Louisiana Immunization Registry, does not have a pharmacy claim with an NDC code indicating a BNT162b2 XBB.1.5 monovalent mRNA vaccine dose and does not have a medical claim with a CPT code indicating a BNT162b2 XBB.1.5 monovalent mRNA vaccine dose will be considered BNT162b2 XBB.1.5 unvaccinated.

BA. 4/5 vaccinations will be enumerated in the same manner as XBB. 1.5.

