
Variable	Role	Data source	Operational definition
			period. Reported as counts and percentages. Note: Death information is available and is sourced from over 40,000 public and private sources nationally. The coverage rate, estimated at over 90% of CDC reported deaths through present day, is based on the number of deaths in the Fact of Death Mortality Index compared to the number of deaths reported by the CDC. Due to HIPAA privacy restrictions, date of death is reported as month and year. Cause of death is not available.

COVID-19 Vaccination Status:

The exposure of interest is the BNT162b2 Bivalent vaccine.

A patient will be considered vaccinated from 14 days after their vaccination date.

The source of the exposure variables are the California and Louisiana vaccine registries and the HealthVerity claims database. Clinical Vaccines Administered code (CVX), National Drug Codes (NDC) and Current Procedural Terminology® (CPT) codes.

BNT162b2 Bivalent vaccinations will be enumerated using the following hierarchical definition:

- Any person in HealthVerity claims data who has a record in the California/Louisiana Immunization Registry with a CVX code indicating having received the BNT162b2 Bivalent vaccine will be considered vaccinated 14 days after registry event date.
- 2. Any person in HealthVerity claims data who does not have a record in the California/Louisiana Immunization Registry but has a pharmacy claim with an NDC code indicating an BNT162b2 Bivalent vaccine dose will be considered vaccinated 14 days after claim date.
- 3. Any person in HealthVerity claims data who does not have a record in the California/Louisiana Immunization Registry and does not have a pharmacy claim with an NDC code indicating an BNT162b2 Bivalent vaccine dose but has a medical claim with a CPT code indicating an BNT162b2 Bivalent vaccine dose will be considered vaccinated 14 days after claim date.

4. Any person in HealthVerity claims data who does not have a record in the California/Louisiana Immunization Registry, does not have a pharmacy claim with an NDC code indicating an BNT162b2 Bivalent vaccine dose and does not have a medical claim with a CPT code indicating an BNT162b2 Bivalent mRNA vaccine dose will be considered BNT162b2 Bivalent unvaccinated.

Patients will be categorized into the following groups based on their COVID-19 vaccination status:

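### As worded, the dose hierarchy consults claims only for people with no registry record of any kind, so a claims-only XBB.1.5 or BA.4/5 dose is not counted for anyone with an earlier registry dose; the likely bias is small and towards the null.

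*SAP*

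**What the plan says.** Section 5.3.1 of the Aim 1 SAP names the two state registries and the claims database as the exposure sources, then lists five rules in order.

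- Rules 1 and 2 need registry evidence of the specific dose. Rule 1 asks for a record in the "Immunization Registry with a CVX code indicating having received the BNT162b2 XBB.1.5 monovalent mRNA vaccine".
- Rule 3 admits a pharmacy claim, but only for a person who "does not have a record in the California/Louisiana Immunization Registry but has a pharmacy claim with an NDC code" for XBB.1.5.
- Rule 4 admits a medical claim, for a person who "does not have a record in the California/Louisiana Immunization Registry and does not have a pharmacy claim with an NDC code" for XBB.1.5.
- Rule 5 defines the unvaccinated. It begins with a person who "does not have a record in the California/Louisiana Immunization Registry, does not have a pharmacy claim with an NDC code" for XBB.1.5, and adds that one who "does not have a medical claim with a CPT code indicating a BNT162b2 XBB.1.5 monovalent mRNA vaccine dose will be considered BNT162b2 XBB.1.5 unvaccinated".

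Rules 2-4 of protocol 8.2 and rules 4-6 of the Aim 2 SAP (5.3.1) use the same condition. Each document extends its list to the bivalent vaccine; the Aim 2 SAP says "BA. 4/5 vaccinations will be enumerated in the same manner as XBB. 1.5". The Aim 3B SAP (5.3, COVID-19 Vaccination Status) applies it directly: its second rule describes the person covered thus: "does not have a record in the California/Louisiana Immunization Registry but has a pharmacy claim with an NDC code indicating an BNT162b2 Bivalent vaccine dose".

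Two other provisions bear on this. Section 5.1 of the Aim 1 SAP sets a default: everyone is unvaccinated from the authorization or approval date until 13 days after a dose, if there is one. Section 5.2 admits people whose claims address is in another state because they have at least one registry record.

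**The concern.** The rules attach the XBB.1.5 qualifier to the NDC and CPT claims but not to the registry record. The registries hold COVID-19 doses of every formulation, so a record from an earlier campaign is enough to block rules 3 to 5.

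The people affected have an earlier dose in the registry and an XBB.1.5 dose that appears only in claims. The out-of-state people admitted under 5.2 are an obvious source. Each has a registry record by construction, while a dose given at home may be known only from a claim. Their post-dose time would be counted as unvaccinated, which pulls VE towards the null.

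The loss would not be equal across the three prior-vaccination subgroups. Relative-VE groups (a) and (b) consist of people with earlier doses, normally in the registry, so claims are not consulted for most of them. The never-vaccinated group normally has no registry record, so claims are used. The same gap in the BA.4/5 history can also move a person with a claims-only bivalent dose out of group (a).

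**Working it through.** **Step 1. Run the rules over every possible person.** Four yes/no facts matter: any registry record, an XBB.1.5 registry record, an NDC claim and a CPT claim for XBB.1.5. Of the 16 combinations, 4 are impossible (an XBB.1.5 record without any record), which leaves 12.

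| Registry | XBB.1.5 claim | Patterns | Rule met as worded | Rule met if the condition is dose-specific |
|---|---|---|---|---|
| None | None | 1 | 5, unvaccinated | 5 |
| None | NDC, with or without CPT | 2 | 3, vaccinated | 3 |
| None | CPT only | 1 | 4, vaccinated | 4 |
| Earlier dose only | None | 1 | none | 5, unvaccinated |
| Earlier dose only | NDC, with or without CPT | 2 | none | 3, vaccinated |
| Earlier dose only | CPT only | 1 | none | 4, vaccinated |
| XBB.1.5 dose | Any | 4 | 1 or 2, vaccinated | 1 or 2 |

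As worded, 4 of 12 patterns match no rule. With a dose-specific condition, all 12 receive exactly one status.

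**Step 2. Apply the default in 5.1.** Of the four unmatched patterns, the one with no claim is correctly unvaccinated under the default. The three with a claim are the real problem. The default ends at receipt of a dose, but receipt is what the hierarchy determines, and the hierarchy does not recognise theirs.

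**Step 3. Planned uptake.** Aim 1 SAP 5.5 gives 0.75 × 12,000,000 × 0.16 × 0.60 = 864,000 adult doses, which reproduces. BNT162b2 uptake is u = 0.16 × 0.60 = 9.6%.

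**Step 4. Dilution.** Let m be the share of recipients whose dose is claims-only and who have an earlier registry record. It is not in the documents and is assumed here.

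- Share of the comparator that is really vaccinated: c = u·m / (1 − u + u·m)
- Observed VE = 1 − (1 − VE) / (1 − VE·c)

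For u = 0.096, m = 0.10 and VE = 40%: c = 0.0096 / 0.9136 = 1.05%, and observed VE = 1 − 0.60 / 0.9958 = 39.75%.

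| m (assumed) | Doses affected | VE 40% reads, u = 9.6% throughout | VE 40% reads, average coverage 4.4% |
|---|---|---|---|
| 5% | 43,200 | 39.87% | 39.94% |
| 10% | 86,400 | 39.75% | 39.89% |
| 20% | 172,800 | 39.50% | 39.78% |
| 50% | 432,000 | 38.77% | 39.45% |

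The last column reflects the SAP's assumption of uniform vaccination from day 14 to the end of follow-up: 0.096 × (168/182) / 2 = 4.4% average coverage.

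**Step 5. Prior-bivalent subgroup.** Protocol 8.5 gives 16% with a bivalent dose, so 0.16 × 9,000,000 = 1,440,000 adults. If every XBB.1.5 recipient came from this group, final uptake there would be 864,000 / 1,440,000 = 60%. That is an upper bound, and averaged over follow-up it is roughly 30%. At 30% and m = 10%, c = 0.03 / 0.73 = 4.1% and a VE of 40% reads 39.0%.

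**Step 6. Registry completeness.** Protocol 8.4.1 compares the registry with the state dashboard: 72.2% against 72.9% for two wild-type doses, and 20.9% against 21.2% for bivalent. The larger relative shortfall is 1 − 20.9/21.2 = 1.4%. This does not measure m, because it does not cover XBB.1.5, Louisiana or doses given out of state. Used as a reference value, m = 1.4% at the 60% bound gives c = 0.0084 / 0.4084 = 2.1% and VE = 39.5%.

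**The case against.** The best defence is that the list enumerates XBB.1.5 vaccinations, so *a record* means an XBB.1.5 record. The naming of claims as an exposure source supports this. So do relative-VE groups (a) and (b), which need previously vaccinated people classed as XBB.1.5 unvaccinated. That is probably what was meant. But the text qualifies the claims and not the registry record, so a programmer who follows it exactly gets the wrong answer. The double programming in protocol 8.8 would not reveal this if both programmers read it the same way.

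The objection on size stands: planned uptake is low, and the protocol describes a nearly complete California registry.

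Three stronger readings are not supported.

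- A reader might infer that previously vaccinated people without XBB.1.5 are unclassified and drop out. The protocol says "We have identified 63% of persons in the claims data have at least one COVID-19 vaccine", and 63% of 9 million adults is 5.67 million, of whom some 4.8 to 5.1 million (53-57% of adults) would match no rule. The default in 5.1 classes them as unvaccinated, so for them the list and the default merely disagree. The 63% also covers all ages and does not count misclassified people.
- A reader might infer a large bias. At 60% uptake the formula gives 36.7% for m = 10% and 33.9% for m = 20%, but those values of m have no source, 60% is an upper bound, and final uptake is treated as if it were person-time.
- A reader might infer that Aim 3B leaves people unclassified. Its three vaccination groups are exhaustive. The effect there is that a claims-only bivalent recipient with a registry record is not placed in the bivalent group.

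**Conclusion.** The point holds as a wording fault that, followed literally, misclassifies claims-only recipients who have an earlier registry dose. It recurs in the protocol and in the SAPs for Aims 1, 2 and 3B.

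For a vaccine that protects, the bias is towards the null and probably small. Overall it is about 0.25 percentage points on a true VE of 40% at 9.6% uptake and an assumed 10% claims-only share, and about 1.2 points if half the doses were claims-only. For scale, Table 5.4 of the Aim 1 SAP gives an interval of 38 to 42 for a VE of 40% at 1,000 cases per 100,000. The loss could be larger in the prior-bivalent subgroup and should be near zero in the never-vaccinated one. A material distortion of the comparison between subgroups is possible but is not shown by any figure in the documents.

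These sizes assume that missed doses are unrelated to the outcome. They also depend on m, which only the data can supply.

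**What to change.** In rules 3-5 of the Aim 1 SAP, rules 4-6 of the Aim 2 SAP, and rules 2-4 of both protocol 8.2 and the Aim 3B SAP, make the registry condition specific: no registry record of a BNT162b2 XBB.1.5 dose (or of a BNT162b2 bivalent dose, where that is the vaccine being enumerated). Claims are then searched for everyone, and the list agrees with the default in 5.1.

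Report the number of doses found only in claims, by prior-vaccination subgroup. That supplies the missing share and shows whether the subgroups were affected unequally.

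The cost is one phrase per hierarchy, the matching line of code and one descriptive output. No new data are needed.

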5.3.2. Outcomes

The outcomes of interest are presented in Table 5.2.

Table 5.2 Outcomes Variables

Outcome Type	Variable	Data source(s)	Operational definition
Primary outcome	COVID-19 diagnosis	HV Claims	Any encounter regardless of diagnosis position or setting with ICD-10-CM code: U07.1.
Secondary outcomes	COVID-19 outpatient encounter	HV Claims	Outpatient encounter with ICD-10-CM code: U07.1
	COVID-19 hospitalization	HV Claims	Hospitalizations "for COVID-19" were defined as those with an inpatient encounter at an acute care facility with ICD-10-CM code U07.1 "COVID-19" that did not have an additional incidental code (for unintentional injury, physical trauma, poisoning, short-stay [<2 days] childbirth or serious psychiatric admissions), or a U07.1 hospitalization where treatment used solely for COVID-19 (eg, remdesivir) was identified regardless of accompanying diagnoses. As a sensitivity analysis, we will restrict this definition to be more conservative by requiring the incidental finding code be the most frequently claimed during the inpatient encounter, as a proxy for primary diagnosis as HealthVerity does not provide this information. As a sensitivity analysis, we will relax this definition to consider any hospitalization with a U07.1 code, without consideration of incidental findings.
	COVID-19 emergency department visit	HV Claims	Emergency department visit with ICD-10-CM code: U07.1

Outcome Type	Variable	Data source(s)	Operational definition
	COVID-19 critical illness	HV Claims	Intensive care unit [ICU] admission, mechanical ventilation, or inpatient death. If sample size allows (Section 5.5), we will evaluate VE against each component separately
	Negative control outcome, such as accidental injury, ingrown toenail or atopic dermatitis	HV Claims	Any encounter regardless of setting, with ICD-10-CM code for negative control outcomes (codes in in the Protocol Annex)
Exploratory outcomes	COVID-19 urgent care encounter	HV Claims	An urgent care encounter with ICD-10-CM code: U07.1 "COVID-19"
	All-cause mortality after COVID-19 encounter	HV Claims and HV Mortality Database	HealthVerity ID in Mortality Database within 3-months of COVID-19 encounter, regardless of setting
	All-cause mortality after COVID-19 outpatient encounter	HV Claims and HV Mortality Database	HealthVerity ID in Mortality Database within 3-months of COVID-19 outpatient encounter
	All-cause mortality after COVID-19 inpatient encounter	HV Claims and HV Mortality Database	HealthVerity ID in Mortality Database within 3-months of COVID-19 inpatient encounter
	All-cause mortality after COVID-19 emergency department encounter	HV Claims and HV Mortality Database	HealthVerity ID in Mortality Database within 3-months of COVID-19 emergency department encounter
	All-cause mortality after COVID-19 critical illness	HV Claims and HV Mortality Database	HealthVerity ID in Mortality Database within 3-months of COVID-19 critical illness

Outcome Type	Variable	Data source(s)	Operational definition
	All-cause mortality after COVID-19 urgent care encounter	HV Claims and HV Mortality Database	HealthVerity ID in Mortality Database within 3-months of COVID-19 urgent care encounter

Each outcome will be assessed independently and experiencing one outcome will not be a censoring event for another outcome. Where a patient has multiple instances of the same outcome, the first one will be used.

As exact dates of death are unavailable, deaths will be classified as occurring within 3 months of the COVID-19 encounter if they occurred in the same calendar month as the encounter or in the next three calendar months.

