- An inpatient encounter with ICD-10-CM U07.1 "COVID-19" listed in any diagnosis position. As a sensitivity analysis, we will restrict to U07.1 in primary diagnosis field.
- An emergency department encounter with ICD-10-CM U07.1 "COVID-19" code
- COVID-19 critical illness, defined as intensive care unit [ICU] admission, mechanical ventilation, or inpatient death. If sample size allows, we will evaluate VE against each component separately in order to support V&E models.

PFIZER CONFIDENTIAL

CT24-WI-GL02-RF02 5.0 Non-Interventional Study Protocol Template For Secondary Data Collection Study 01-Aug-2023

Negative control outcomes such as accidental injury, ingrown toenail or atopic dermatitis

Exploratory outcomes:

- An urgent care encounter with ICD-10-CM U07.1 "COVID-19" code
- All-cause mortality within 3-months of COVID-19 encounter, regardless of setting
- All-cause mortality within 3-months of COVID-19 outpatient encounter
- All-cause mortality within 3-months of COVID-19 inpatient encounter
- All-cause mortality within 3-months of COVID-19 emergency department encounter
- All-cause mortality within 3-months of COVID-19 critical illness
- 7. All-cause mortality within 3-months of COVID-19 urgent care encounter

Measures of absolute and relative VE: For each outcome above, results will be calculated as:

- 1. Absolute VE comparing vaccinated to unvaccinated persons, regardless of prior vaccination
- Relative VE will be calculated for each of the following mutually exclusive subgroups.
 - xBB.1.5 vaccinated vs xBB.1.5 unvaccinated persons who received BA.4/5 bivalent vaccine.
 - b. XBB.1.5 vaccinated vs XBB.1.5 unvaccinated persons who did not receive BA.4/5 bivalent vaccine but did receive at least 2 doses of mRNA vaccine (regardless of formulation).
 - xBB.1.5 vaccinated vs never COVID-19 vaccinated.

Stratifications: Results will be stratified by age group (overall, age 18-49, 50-64, 65+) as well as by calendar time (BA.4/5 versus XBB.1.5 vaccine available eras).

[figure not shown]

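### Aim 1 SAP: the hospitalization sensitivity analysis labelled more conservative, read literally, loosens the definition, so no planned variant is stricter than the main one

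*SAP*

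**What the plan says.** **Protocol, section 8.7.1 (Aim 1).** The inpatient outcome is an admission with U07.1 in any diagnosis position. One stricter check is planned: "As a sensitivity analysis, we will restrict to U07.1 in primary diagnosis field".

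**Aim 1 SAP, section 5.3.2, Table 5.2.** The main definition is tightened. An acute-care admission with U07.1 counts if it is one "that did not have an additional incidental code (for unintentional injury, physical trauma, poisoning, short-stay [<2 days] childbirth or serious psychiatric admissions"). An admission with U07.1 also counts where "treatment used solely for COVID-19 (eg, remdesivir) was identified regardless of accompanying diagnoses".

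Two sensitivity analyses of this outcome follow:

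- The first is described as a restriction that makes the definition more conservative, by "requiring the incidental finding code be the most frequently claimed during the inpatient encounter". The stated reason is that claim frequency serves "as a proxy for primary diagnosis as HealthVerity does not provide this information".
- In the second, "we will relax this definition to consider any hospitalization with a U07.1 code, without consideration of incidental findings".

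**Aim 1 SAP, section 5.7.7.** The examples given here are a 7-day exposure window and a 3-month follow-up. Neither changes the outcome definition.

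**The concern.** The first sensitivity analysis is presented as a restriction and the second as a relaxation, so a reader expects one variant on each side of the main definition. The first, however, attaches its extra requirement to the incidental code, which is the criterion that removes admissions. Making that criterion harder to meet removes fewer of them.

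The main definition removes only the listed categories: unintentional injury, physical trauma, poisoning, short-stay childbirth and serious psychiatric admissions. An admission for some other unrelated reason that also carries U07.1 remains an event. If such admissions have a lower VE than admissions caused by COVID-19, they dilute the hospitalization VE. A definition stricter than the main one is the way to look for this. If the only variants are looser, agreement among the three results could be read as support from a more conservative analysis that was not in fact run.

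**Working it through.** No figure in the plan needs reproducing. The check is one of set inclusion, with every rule taken from Table 5.2 of the Aim 1 SAP.

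**Step 1. Describe each U07.1 admission by four yes/no features:** incidental code present; incidental code most frequent; U07.1 most frequent; COVID-only treatment found. An incidental code cannot be the most frequent if it is absent. Ignoring ties, the incidental code and U07.1 cannot both be most frequent. Ten states remain.

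**Step 2. Apply each definition.** The first variant is read as excluding an untreated admission only when the incidental code is the most frequent.

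| Admission type | States | Main | First variant | Any U07.1 | U07.1 most frequent, within main |
|---|---|---|---|---|---|
| No incidental code | 4 | 4 | 4 | 4 | 2 |
| Incidental code present but not most frequent, treated | 2 | 2 | 2 | 2 | 1 |
| Incidental code present but not most frequent, untreated | 2 | 0 | 2 | 2 | 0 |
| Incidental code most frequent, treated | 1 | 1 | 1 | 1 | 0 |
| Incidental code most frequent, untreated | 1 | 0 | 0 | 1 | 0 |
| **Total** | **10** | **7** | **9** | **10** | **3** |

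Every state in the main set is in the first variant, and every state in the first variant is in any U07.1. Both planned variants are therefore supersets of the main definition. The last column is a true subset. These are counts of logical states, not shares of admissions.

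**Step 3. Express the same result as event counts.** Let N be the number of U07.1 admissions, p the share that are untreated with an incidental code, and q the share of those in which that code is the most frequent.

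- Main: N(1 − p)
- First variant: N(1 − pq)
- Any U07.1: N
- First variant minus main: Np(1 − q), which is never negative

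The documents give neither p nor q. Assume, for illustration only, N = 1000, p from 10% to 30% and q from 25% to 75%:

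- Main: 1000 × (1 − 0.30) = 700 up to 1000 × (1 − 0.10) = 900
- First variant: 1000 × (1 − 0.30 × 0.75) = 775 up to 1000 × (1 − 0.10 × 0.25) = 975
- Any U07.1: 1000
- Added by the first variant: 1000 × 0.10 × 0.25 = 25 up to 1000 × 0.30 × 0.75 = 225

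**Step 4. Try other readings of the sentence.**

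- Count only admissions where the incidental code is most frequent, keeping the treated ones. This gives 6 states, not nested in the main set, and it selects incidental admissions.
- Add that requirement on top of the main definition. One state is left: treated admissions dominated by an incidental code. The set is smaller but makes no sense as a COVID-19 outcome.
- Move the requirement to U07.1. This gives the 3-state subset above, the only reading tested that is sensibly stricter.

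**The case against.** The strongest reply is that this is a drafting slip. The wish to restrict, and the reference to primary diagnosis, suggest that the frequency requirement was meant for U07.1, which would make the analysis stricter. That may well be the intent, but the text does not say so, and a programmer following it would build the looser set. Alternatively, conservative might mean cautious about calling an admission incidental, or a VE nearer the null. But what is to be restricted is the hospitalization definition itself, and the next sentence sets a relaxation against it. Under those readings the analysis would still be a relaxation and need a new label.

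Other parts of the reply stand, and they rule out stronger conclusions that a reader might draw:

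- **That specificity is never tested.** The documents do not support this. The SAP's main definition is already tighter than the protocol's any-position outcome, and comparing it with any U07.1 shows what happens when coded incidental admissions are removed. The gap is only on the stricter side of the main definition.
- **That this sentence is why the protocol's primary-field check was lost.** The SAP gives a different reason: HealthVerity does not supply that field. The fault is that the replacement does not do the same job.
- **That hospitalization VE is understated by some number of points.** Any such figure needs an incidental share and separate VEs for incidental and causal admissions, none of which the documents give. The 20 to 40% in section 5.5 of the Aim 1 SAP is anticipated from symptomatic infection.
- **That Aim 2 contains the same error.** Its SAP has only the relaxation to any U07.1, and labels it correctly.

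A stricter rule is also not automatically less biased. For influenza, the protocol (section 8.7.6) warns that primary coding may favour complications over the infection. The same could happen with COVID-19.

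**Conclusion.** The point holds for the Aim 1 SAP. Taken literally, the restricting analysis moves in the opposite direction to its label, both outcome-definition variants are looser than the main definition (7, 9 and 10 of 10 states), and no named analysis is stricter. Critical illness is a separate outcome and does not fill the gap. The nesting needs no numerical assumption. It rests on reading the requirement as a narrowing of the exclusion, and the other literal readings do not give a usable stricter outcome either.

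The consequence is limited. Residual incidental admissions outside the listed categories go unexamined. Hospitalization is a secondary outcome, so the primary Aim 1 result is untouched. The size of any effect on VE cannot be derived from the documents, and its direction depends on incidental admissions having the lower VE. The change should be made, but it does not put the study's main conclusion in doubt.

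**What to change.** In Table 5.2 of the Aim 1 SAP, replace the first sensitivity analysis with one that keeps the main definition and also requires U07.1, not the incidental code, to be the most frequently claimed diagnosis code during the inpatient encounter, as the proxy for primary diagnosis. State how ties are handled. Relabel the present rule as an intermediate relaxation between the main definition and any U07.1, or drop it.

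The cost is one sentence and a change to the selection logic, using claims already held. That analysis will have fewer events, and it may drop true COVID-19 admissions billed mainly under complications. It should therefore be reported as a sensitivity analysis only, with that limitation stated. Adding the same analysis to the Aim 2 SAP is optional. It would provide a stand-in for the primary-field check that the protocol also lists for that aim, but there is no mislabelled rule there to correct.
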